6.2. Timing of Analyses

The final CSR will be completed after the last subject’s last visit is completed, and the final clinical database including all long-term safety follow-up data is cleaned, monitored and locked. The primary CSR will include results for all primary and secondary endpoint data as well as exploratory EBOV GP pseudovirion neutralization assay data. Additional results for exploratory endpoint data will be included as one or more addenda to the primary CSR.

6.3. Analysis Populations

6.3.1. The Safety Analysis Population

The Safety Analysis population includes all subjects who received at least one study vaccination.

6.3.2. The Intent-to-Treat (ITT) Analysis Population

The ITT population includes all subjects who received at least one study vaccination and contributed both pre- and at least one post-study vaccination blood samples for immunogenicity testing for which valid results were reported. Subjects will be analyzed according to the study group to which they were randomized.

6.3.3. The Per Protocol (PP) Analysis Population

The per protocol (PP) population includes all subjects in the ITT subset with the following exclusions:

- Data from all available visits for subjects found to be ineligible at baseline.
- Data from all visits subsequent to major protocol deviations, such as:
 - Second study vaccination not received,
 - Receipt of non-study licensed live vaccine within 30 days prior to or after each study vaccination,
 - Receipt of non-study licensed inactivated vaccine within 14 days prior to or after each study vaccination,
 - Receipt of oral or parenteral (including intraarticular) corticosteroids of any dose within 30 days prior to study vaccination.
 - Receipt of high-dose inhaled corticosteroids within 30 days prior to study vaccination.

- Receipt of chronic (defined as more than 14 days) immunosuppressants or other immune modifying drugs within 6 months of receipt of study vaccine.
- Data from any visit that occurs outside the pre-defined protocol window.
- In the case of mis-randomization, subjects will be analyzed according to the study product actually received.

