6.6. Concomitant Medications/Treatments

Administration of any medications, therapies, or vaccines will be recorded on the appropriate data collection form. Concomitant medications will include all current medications and medications taken within 60 days prior to signing the informed consent form through approximately 28 days after the second study vaccination or early termination (if prior to 28 days

after the second study vaccination), whichever occurs first. Assessment of study eligibility will include a review of all permitted and prohibited medications per the Subject Inclusion and Exclusion Criteria (see [Section 5](#)). Medications reported in the electronic case report form (eCRF) are limited to those taken within 30 days prior to study vaccination through approximately 28 days after the second study vaccination. Prescription and over-the-counter drugs will be included as well as herbals, vitamins, and supplements. In addition, receipt of non-study vaccines will be solicited through approximately 28 days after the second study vaccination, and reported in the eCRF.

Use of new medication should prompt evaluation for the occurrence of an AE or worsening of a pre-existing medical condition.

Medications that might interfere with the evaluation of the investigational product(s) should not be used from time of study vaccination through 28 days post the second vaccination unless clinically indicated as part of the subject's health care. Medications in this category include the prohibited medications per the Subject Exclusion Criteria (see [Section 5.2](#)). In addition, the site principal investigator or appropriate sub-investigator may identify other medications that should not be used due to a risk to subject safety or assessment of reactogenicity and immunogenicity. Use of medications as prophylaxis prior to study vaccination is prohibited. There are no known drug-vaccine interactions with the study vaccine and subjects are not being asked to discontinue current medications not listed in the exclusion criteria. In the event medical conditions dictate use of medications, subjects are encouraged to obtain adequate care, comply with the course of therapy as prescribed by their physician and inform the site as soon as practicable. Details of all medications taken during the medication reporting period for this study (date, indication, brand or generic name) will be recorded.

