	Receipt of non-study licensed live vaccine within 30 days prior to or after each study vaccination [#]	x	x.x	x	x.x	x	x.x
	Receipt of non-study licensed inactivated vaccine within 14 days prior to or after each study vaccination [#]	x	x.x	x	x.x	x	x.x
	Receipt of oral or parenteral (including intraarticular) corticosteroids of any dose within 30 days prior to study vaccination [#]	x	x.x	x	x.x	x	x.x
	Receipt of high-dose inhaled corticosteroids within 30 days prior to study vaccination [#]	x	x.x	x	x.x	x	x.x
	Receipt of chronic (defined as more than 14 days) immunosuppressants or other immune modifying drugs within 6 months of receipt of study vaccine [#]	x	x.x	x	x.x	x	x.x
	Data from any visit that occurs outside the pre-defined protocol window. [#]	x	x.x	x	x.x	x	x.x

N=Total number of enrolled subjects.

*: In the case of mis-randomization, subjects will be analyzed according to the study product actually received.

[#]: These rules may result in subsets of visits to be excluded (visits subsequent to the respective deviation). These are only counted in this table if the visit exclusion resulted in excluding all visits and thus the complete subject. For individual per-visit exclusions, see Table 13.

Table 13: Per-Protocol Analysis Population Visit Exclusions by Study Arm and Study Visit Day

Study Visit Day	Reason Subjects Excluded	Study Arm 1 (ChAd3+Placebo) (N=X)		Study Arm 2 (ChAd3+ChAd3) (N=X)		Study Arm 3 (ChAd3+MVA-BN) (N=X)		All Subjects (N=X)	
		n	%	n	%	n	%	n	%
Day 1	Any Reason	x	x.x	x	x.x	x	x.x	x	x.x
	First study vaccination not received	x	x.x	x	x.x	x	x.x	x	x.x
Day 8 (Second Vaccination)	Any Reason	x	x.x	x	x.x	x	x.x	x	x.x
	First study vaccination not received	x	x.x	x	x.x	x	x.x	x	x.x
	Data from all available visits for subjects found to be ineligible at baseline.	x	x.x	x	x.x	x	x.x	x	x.x
	Second study vaccination not received	x	x.x	x	x.x	x	x.x	x	x.x
	Receipt of non-study licensed live vaccine within 30 days prior to or after each study vaccination	x	x.x	x	x.x	x	x.x	x	x.x
	Receipt of non-study licensed inactivated vaccine within 14 days prior to or after each study vaccination	x	x.x	x	x.x	x	x.x	x	x.x
	Receipt of oral or parenteral (including intraarticular) corticosteroids of any dose within 30 days prior to study vaccination	x	x.x	x	x.x	x	x.x	x	x.x
	Receipt of high-dose inhaled corticosteroids within 30 days prior to study vaccination	x	x.x	x	x.x	x	x.x	x	x.x

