	Receipt of chronic (defined as more than 14 days) immunosuppressants or other immune modifying drugs within 6 months of receipt of study vaccine	x	x.x	x	x.x	x	x.x	x	x.x
	Data from any visit that occurs outside the pre-defined protocol window.	x	x.x	x	x.x	x	x.x	x	x.x

N=Total number of enrolled subjects.

Table 14: Subject Disposition by Treatment Group

Subject Disposition	Study Arm 1 (ChAd3+Placebo) (N=X)		Study Arm 2 (ChAd3+ChAd3) (N=X)		Study Arm 3 (ChAd3+MVA-BN) (N=X)		All Subjects (N=X)	
	n	%	n	%	n	%	n	%
Screened	--	--	--	--	--	--	x	--
Enrolled/Randomized	x	100	x	100	x	100	x	100
Received First Vaccination	x	x.x	x	x.x	x	x.x	x	x.x
Received First and Second Vaccination ^a	x	x.x	x	x.x	x	x.x	x	x.x
Received Second Vaccination Out of Window	x	x.x	x	x.x	x	x.x	x	x.x
Completed Day 1 Blood Draw	x	x.x	x	x.x	x	x.x	x	x.x
Completed Day 8 Blood Draw ^b	x	x.x	x	x.x	x	x.x	x	x.x
Completed Day 8 Post-Second Vaccination Blood Draw	x	x.x	x	x.x	x	x.x	x	x.x
Completed Day 15 Post-Second Vaccination Blood Draw	x	x.x	x	x.x	x	x.x	x	x.x
Completed Day 22 Post-Second Vaccination Blood Draw	x	x.x	x	x.x	x	x.x	x	x.x
Completed Day 29 Post-Second Vaccination Blood Draw	x	x.x	x	x.x	x	x.x	x	x.x
Completed Follow-up (Study Day 182 ^a	x	x.x	x	x.x	x	x.x	x	x.x
Completed Per Protocol ^c	x	x.x	x	x.x	x	x.x	x	x.x

N=Total number of enrolled subjects.

^aRefer to Listing 2 for reasons subjects discontinued or terminated early.^bBlood drawn prior to second vaccination^cRefer to Listing 5 for reasons subjects are excluded from the per protocol population

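### The named per-protocol exclusions do not cover corticosteroids after the second vaccination or an out-of-window boost, and Table 13 applies the no-second-dose reason to a sample drawn before the boost

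*SAP*

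**What the plan says.** SAP 6.3.3 and protocol 11.4.1 define the PP population in the same terms. They start from ITT and remove "Data from all visits subsequent to major protocol deviations, such as" a list of items. The relevant items are:

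- live and inactivated non-study vaccines, counted both before and after each study vaccination;
- systemic corticosteroids, worded as "Receipt of oral or parenteral (including intraarticular) corticosteroids of any dose within 30 days prior to study vaccination";
- inhaled corticosteroids at high dose, with the same 30-day look-back and no forward limit;
- immunosuppressants and similar drugs used for more than 14 days, with a 6-month window around the study vaccine;
- failure to receive the second vaccination.

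A separate rule removes "Data from any visit that occurs outside the pre-defined protocol window".

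Protocol 6.6 says that medications that might interfere with evaluation "should not be used from time of study vaccination through 28 days post the second vaccination unless clinically indicated". It places the drugs barred by the exclusion criteria in that category, and both corticosteroid types are among them.

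The boost visit (V06) is Day 8 with an allowance of two days. Later visits are timed from the second vaccination (protocol 7.3.2, 7.3.3). SAP Table 14 has a row "Received Second Vaccination Out of Window" and Listing 8 a matching column. SAP Tables 12 and 13 give the PP exclusion reasons. In the Day 8 block of Table 13, one reason is "Second study vaccination not received".

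**The concern.** A PP set should hold the titres of subjects who received the regimen as designed, free of interfering treatment. Three features work against that.

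1. The steroid items stop at vaccination, so a course taken while the post-boost response develops triggers no named exclusion. The vaccine items beside them do look forward, and protocol 6.6 is concerned about these drugs until 28 days after dose 2.
2. The short prime-boost interval is part of one of the two major objectives (protocol 2.2, SAP 2.3). A subject boosted outside the window did not receive that interval, yet the rules do not say whether the later titres count.
3. A subject who misses the boost still has a valid Day 8 sample after one dose of ChAd3-EBO-Z, and Day 8 is summarised with the three arms pooled. Table 13 would allow that sample to be dropped.

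All antibody analyses are run in PP as well as ITT (SAP 8.1). If the handling is left open, it may be settled after titres and assignments are known.

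**Working it through.** The plan states no figure on this point, so the check sets the rules against the visit calendar. Days are counted from the first vaccination as Day 1, on a continuous scale that includes Day 0.

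**Steroid items.** Inputs: first vaccination on Day 1, boost on Day *b* from 8 to 10, and a look-back of 30 days before either vaccination.

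| Boost day | Start days caught | Start days not caught, to nominal V11 | Nominal V08, V09, V10, V11 |
|---|---|---|---|
| 8 | -29 to 7 | 8 to 36 | 15, 22, 29, 36 |
| 9 | -29 to 8 | 9 to 37 | 16, 23, 30, 37 |
| 10 | -29 to 9 | 10 to 38 | 17, 24, 31, 38 |

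Use between the doses is caught, because it falls within 30 days before the second vaccination. Use from the boost onward is not, and that 29-day span contains every post-boost titre visit.

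**Out-of-window boost.** Inputs: the V08 window is Day 8 to 9 after dose 2 and the V11 window is Day 27 to 31. Counted from dose 1, V08 runs from *b* + 7 to *b* + 8, and V11 from *b* + 26 to *b* + 30.

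- *b* = 8: V08 on Days 15 to 16, V11 on Days 34 to 38.
- *b* = 10: V08 on Days 17 to 18, V11 on Days 36 to 40.
- *b* = 14 (illustrative, out of window): V08 on Days 21 to 22, V11 on Days 40 to 44.

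Because these windows move with dose 2, the post-boost visits stay in window however late the boost is. As 6.3.3 is worded, the window rule removes V06 alone. Table 12, however, attaches a footnote to that same rule, saying that the flagged rules can remove the visits following the deviation. The two texts give different data sets for the same subject.

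**Day 8 block of Table 13.** Protocol 7.3.2 and the Table 14 footnote place the Day 8 draw before the second vaccination. The 6.3.3 rule acts on visits after the deviation. A second dose that is not given cannot precede a sample drawn ahead of it, so the table entry contradicts the rule.

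**Size.** If one subject in an arm of 20 has a titre lower by a factor *r*, the arm's geometric mean titre falls by a factor *r*^(1/20):

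- *r* = 2: 1.035
- *r* = 4: 1.072
- *r* = 10: 1.122

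Over the range of *r* this is a shift of 3.5% to 12%. Taken as a fall from the unaffected mean, it is 1 − 1/1.035 = 3.4% to 1 − 1/1.122 = 10.9%. The range of *r* is an assumption.

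**The case against.** **The list is open.** It gives examples, so a post-boost steroid course or a late boost could still be classed as a major deviation, and Tables 12 and 13 are only mock-ups. That is fair, and it means the plan cannot be said to keep these titres. But the open list reaches only major protocol deviations. Protocol 6.6 allows the drugs when clinically indicated, so such a course may not be a deviation at all. A late boost is a deviation, since protocol 5.4.3 rules out vaccination outside the window, but nothing says that it counts as major.

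**The Table 12 footnote already covers late boosts.** A reader might infer that every post-boost titre is certain to stay in PP. The documents do not support that, because the footnote points the other way. What stands is that 6.3.3 and the footnote disagree.

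**Immunosuppressants.** A reader might infer that use after vaccination is missed here too. The item reads "Receipt of chronic (defined as more than 14 days) immunosuppressants or other immune modifying drugs within 6 months of receipt of study vaccine", and its window is not limited to prior use, so on a plain reading later chronic use is covered. Only its direction should be stated.

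**All steroid use after dose 1.** It is also tempting to say that this goes uncaught. As shown above, use between the doses is caught, and disallowed medication before dose 2 also bars that dose under protocol 5.4.3.

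**Bias.** Removing data because of post-randomisation treatment can itself bias arm comparisons. This is true, but it applies equally to the existing PP items on vaccines and missed doses, and ITT is reported alongside.

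**The Table 13 entry is a repeated template block.** Probably so, and the text of 6.3.3 should govern. The entry still contradicts it.

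**Conclusion.** The point holds as a gap and two inconsistencies in the analysis-set rules. Corticosteroid use after dose 2 is not among the named exclusions. The handling of titres after an out-of-window boost differs between 6.3.3 and the Table 12 footnote. The Day 8 block of Table 13 carries a reason that the rule does not allow.

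The impact is minor. The documents give no expected number of affected subjects. The shift per subject rests on an assumed 2- to 10-fold titre reduction and 20 subjects per arm. For scale, with an assumed log10 SD of 0.3 to 0.6, the 95% interval for a 20-subject geometric mean titre extends by a factor of 10^(2.093 × 0.3/√20) = 1.38 to 10^(2.093 × 0.6/√20) = 1.91 on each side, so one affected subject lies well inside it. The primary endpoints are safety endpoints in the Safety population, PP stands beside ITT for secondary and exploratory antibody results, and no formal hypothesis is tested. A reader might conclude that PP is a contaminated population. The documents do not support that, since they do not show that any such titre exists or would be retained.

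**What to change.** Before unblinding, make these changes in SAP 6.3.3 and protocol 11.4.1. They concern only which data enter the PP analysis and alter no rule on treatment or vaccination.

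- **(a) Corticosteroids.** Extend only the two corticosteroid items to cover use through 28 days after the second vaccination, excluding visits after that use. Leave the 6-month immunosuppressant window as it is, and state that it covers use before and after vaccination. Replacing it with the steroid window would shorten its look-back from 6 months to 30 days.
- **(b) Boost timing.** Add a second vaccination given outside the protocol window as a PP reason that excludes subsequent visits. State explicitly what happens to the pre-boost sample from that visit, and make 6.3.3 and the Table 12 footnote agree.
- **(c) Day 8.** Delete "Second study vaccination not received" from the Day 8 block of Table 13, and update Tables 12 and 13 for (a) and (b).

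The cost is a few lines of text in two documents and possibly a few PP observations. If unblinding has already taken place, record the decision and its timing in the clinical study report, as SAP section 1 provides for deviations from the plan.

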6.4. Covariates and Subgroups

There is no *a priori* plan to adjust the analyses of safety and immunogenicity for covariates or carry out subgroup analyses.

6.5. Missing Data

Unless otherwise specified, missing data will be maintained as missing for all analyses and no imputation will be performed for missing values.

6.6. Interim Analyses and Data Monitoring

6.6.1. Interim Safety Review

Interim safety reviews were not conducted.

6.6.2. Interim Immunogenicity Review

An interim immunogenicity review was not planned.

6.7. Multicenter Studies

This is a single center study.

6.8. Multiple Comparisons/Multiplicity

The study was not designed to test any specific null hypothesis. No multiple testing adjustments will be carried out for immunogenicity endpoints. For high-dimensional exploratory -omics endpoints, the false discovery rate (FDR) will be used to control the number of false discoveries [29]. See SAP addendum for further details.

7. STUDY SUBJECTS

7.1. Disposition of Subjects

A flowchart presenting the disposition of study subjects, adapted from the CONSORT statement will be included ([Figure 1](#)). The flowchart includes the number of subjects eligible, enrolled and randomized, lost to follow-up, and analyzed, by study arm. The disposition of subjects in the study will be tabulated by treatment group as shown in [Table 14](#). The number of enrolled subjects and per-visit exclusions will be summarized by analysis population ([Table 12](#) and [Table 13](#)). Screened subjects who were ineligible for enrollment in the study will be presented by inclusion and exclusion criteria ([Table 11](#)). A listing of subjects who discontinued or terminated early from the study will be included in [Listing 2](#). Subjects and per-visit exclusions will be provided in [Listing 5](#).

7.2. Protocol Deviations

A summary of protocol deviations will be presented by the deviation category, type, and treatment group in [Table 3](#). This table will provide both the number of subjects and the number of deviations for each category and study arm. All subject-specific protocol deviations and non-subject-specific protocol deviations will be provided in [Listing 3](#) and [Listing 4](#), respectively.

8. IMMUNOLOGY EVALUATION

8.1. Antibody Analyses

The primary immunogenicity antibody endpoint analysis will be based on anti-EBOV GP ELISA titer. Exploratory endpoint analysis will assess anti-EBOV neutralizing antibody titers (anti-EBOV GP NEUT50 and anti-EBOV GP NEUT40). All antibody analyses will be conducted for both the ITT and PP analysis populations. Subject level antibody data for anti-EBOV GP ELISA and anti-EBOV GP NEUT will be presented as shown in [Listing 9](#).

For each study arm and analysis population, titers for each study visit will be summarized by tabulating the number of observations, geometric mean and 95% CI of the geometric mean (based on Student's t-distribution) ([Table 18](#)). Per-visit geometric mean titers and 95% CIs will be visualized across study visits by study arm using time trend plots as presented in [Figure 2](#). Similarly, the geometric mean fold rise relative to pre-vaccination (Day 1) will be summarized ([Table 19](#) and [Figure 2](#)). For each study arm and analysis population, the number of subjects that achieved seroconversion for each post-first vaccination study visit will be summarized by tabulating numbers, percentages, and associated 95% CIs (based on Clopper-Pearson) ([Table 20](#)). Per-visit seroconversion percentages and 95% CIs will be visualized across post-first vaccination study visits by study arm using time trend plots as presented in [Figure 3](#). For the exploratory assessment of neutralization titers (anti-EBOV GP NEUT50 and anti-EBOV GP NEUT40), GMTs and GMFRs will be tabulated and visualized as presented in [Table 18](#), [Table 19](#), and [Figure 2](#).

Significant differences in anti-EBOV GP ELISA and anti-EBOV neutralizing antibody titers (anti-EBOV GP NEUT50 and anti-EBOV GP NEUT40) between study groups for each post-second vaccination time points will be evaluated using a two-sided Welch's t-test using an individual alpha of 0.05 ([Table 21](#)). Differences in anti-EBOV GP ELISA-based seroconversion at post-second vaccination time points will be assessed using a two-sided Fisher's exact test using an individual alpha of 0.05 ([Table 22](#)).

9. SAFETY EVALUATION

All safety analyses will be presented using the safety population. Any medical condition that is present at the time that the subject is screened will be considered baseline and not reported as an AE, unless it worsens in severity or increases in frequency during the study. When calculating the incidence of solicited and unsolicited adverse events (i.e., on a per subject basis), each subject will be counted once and any repetitions of solicited and unsolicited adverse events within a subject will be ignored; the denominator will be the number of subjects in the safety analysis population unless results are shown by dose in which case the denominator will be the number of subjects that received the respective dose.

